## ***21.6 Grade of adverse events***

Grade referred to the severity of the adverse event. CTCAE v4.0 displays grades 1 through 5 with unique clinical descriptions of severity for each adverse event based on the general guidelines. A serious adverse event is defined as any of the following toxicities identified during the 6 months of treatment:

- Grade  $\geq 3$  of any adverse events;
- Persistent hypotension;
- Persistent bradycardia; and
- Intolerable CNS-related adverse effects.

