## 5 Study background and rationale

IHs are the most common tumors of childhood and occur in approximately 4% to 5% of infants. In the majority of cases, IHs are self-limited and resolve spontaneously without threat or complications. However, in approximately 10% of patients, the lesions can be disfiguring (e.g., facial involvement), destructive (e.g., ulceration), functionally significant (e.g., visual impairment), or even life-threatening (e.g., airway obstruction).

Currently, propranolol is the preferred treatment for problematic proliferating IHs. Although propranolol is clearly efficacious, rare adverse effects, such as hypoglycemia and bronchial hyperreactivity, may be life-threatening. Nonselective  $\beta$ -adrenergic antagonists, such as propranolol, are competitive antagonists of catecholamines at the  $\beta_1$ - and  $\beta_2$ -adrenergic receptors (ARs).  $\beta_2$ -AR blockade may result in hypoglycemia as a result of decreased glycogenolysis, gluconeogenesis, and lipolysis. Moreover, bronchial hyperreactivity is a direct effect of propranolol that results in bronchospasms due to pulmonic  $\beta_2$ -AR blockade. In addition, the lipophilic nature of propranolol is also important. When given to infants, the long-term effects of propranolol may affect the developing central nervous system (CNS), specifically learning and memory.

A solution to minimize some of the side effects of propranolol may be the use of more selective  $\beta_1$ -AR blockers, such as atenolol, which, at low dosages, have little  $\beta_2$  activity. More importantly, atenolol is a large, hydrophilic compound and may exhibit fewer CNS-related adverse effects (e.g., sleep disturbance and agitation) in the treatment of IHs. Unfortunately, there is a paucity of clinical data comparing the efficacy and safety of propranolol and atenolol.

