## ***21.8 Termination of the study***

All participants were informed that they had the right to withdraw from the study at any time without prejudice to their medical care and that they were not obliged to state their reasons. Follow-up was considered complete when the participant completed all study procedures and assessments up to the 96-week visit. Termination of the study was mandatory in the following situations:

- Any grade  $\geq 4$  adverse event;
- Recurrent or persistent cases of hypoglycemia, bronchitis with dyspnea, bronchial hyperreactivity or bronchospasms.
- Persistent hypotension; or

---

-Persistent bradycardia.

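### Sections 21.6 and 21.8 do not match: recurrent or persistent hypoglycemia and bronchial events force termination at any grade but are serious only from grade 3, so serious-event counts by arm may understate a beta-2 difference

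*Combined protocol and SAP*

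**What the plan says.** Section 21.6 defines a serious event by a closed list: "A serious adverse event is defined as any of the following toxicities identified during the 6 months of treatment". The list has four entries:

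- grade 3 or higher "of any adverse events";
- "Persistent hypotension";
- persistent bradycardia;
- "Intolerable CNS-related adverse effects".

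Only the first entry carries a grade threshold.

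Section 21.8 says "Termination of the study was mandatory in the following situations" and gives four triggers: any event of grade 4 or higher, persistent hypotension, persistent bradycardia, and "Recurrent or persistent cases of hypoglycemia, bronchitis with dyspnea, bronchial hyperreactivity or bronchospasms". The last trigger has no grade threshold.

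Section 5 says of propranolol that "rare adverse effects, such as hypoglycemia and bronchial hyperreactivity, may be life-threatening". It explains both effects by beta-2 blockade and says that atenolol has little beta-2 activity at low dosages.

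Section 21.3 analyzes all events judged at least possibly related to treatment. For each event it gives the percentage of subjects in each group with one or more occurrences, and it compares events over the first 24 weeks. Section 25.5 lists premature discontinuations with group, time and reason.

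**The concern.** An infant with recurrent grade 2 bronchospasm must be terminated but has no serious adverse event. An infant with persistent grade 2 bradycardia must also be terminated and does have one. The plan gives no reason for the different treatment.

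The gap is one the protocol itself foresees. Section 21.7 anticipates mild hypoglycemia and mild to moderate bronchospasm, with temporary interruption suggested, and section 21.8 escalates to termination when such events recur or persist.

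The omitted class is also not neutral between arms. By the reasoning in section 5, these are the harms that a beta-1 selective drug should reduce. A reader who looks to the serious-event count for the safety contrast would not see the lower-grade part of that difference, even where the event was enough to end participation.

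**Working it through.** The plan states no serious-event rate and no rate of hypoglycemia or bronchospasm, so there is no figure to reproduce. The check sets the lists side by side.

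**Step 1. Termination triggers (21.8) against the serious-event list (21.6).**

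| Trigger in 21.8 | Serious under 21.6? |
|---|---|
| Any event of grade 4 or higher | Always (inside grade 3 or higher) |
| Persistent hypotension | Always, any grade |
| Persistent bradycardia | Always, any grade |
| Recurrent or persistent hypoglycemia or bronchial events | Only at grade 3 or higher |

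Three of the four triggers lie wholly inside the serious-event definition. The fourth lies inside it only in part, and the part left out is grades 1 and 2.

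**Step 2. The reverse direction.** Intolerable CNS effects are serious at any grade but are not a mandatory trigger in 21.8; section 21.7 only recommends discontinuation. Section 5 expects fewer CNS effects on atenolol. So one any-grade entry on the serious list does capture an expected propranolol harm.

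**Step 3. Where the omitted events still appear.**

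- Section 21.3 includes them at any grade if judged at least possibly related, so no affected infant is lost from that comparison. Its measure is one or more occurrences per subject. One mild episode and a recurrent course that ends in termination each add one to the same percentage.
- Section 25.5 shows a resulting premature discontinuation in a listing with group and reason, but specifies no summary or comparison by arm.
- No comparison or test of serious events is specified in 21.3 or 25.5.

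**Step 4. Scale, on assumed rates only.** With the planned 180 per arm (section 12), the expected number of infants left out of the serious count is 180 × the rate of recurrent or persistent events that never reach grade 3. The rates below are assumptions.

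| Assumed rate, propranolol / atenolol | Left out, propranolol | Left out, atenolol | Shift in rate difference |
|---|---|---|---|
| 0.5% / 0% | 180 × 0.005 = 0.9 | 0 | 0.5 points |
| 1% / 1% | 180 × 0.01 = 1.8 | 1.8 | 0 |
| 2% / 0.5% | 180 × 0.02 = 3.6 | 180 × 0.005 = 0.9 | 1.5 points |
| 3% / 1% | 180 × 0.03 = 5.4 | 1.8 | 2 points |
| 5% / 1% | 180 × 0.05 = 9.0 | 1.8 | 4 points |

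Even the top row of effect, 5% against 1%, would be hard to establish by a test. If events already on the list run at 2% in both arms, the totals become 7% and 3%, and a two-sided 5% comparison with 180 per arm has about 41% power. If listed events run at 5%, the totals are 10% and 6%, with about 29% power. The point is therefore about describing harms fully, not about a test that would change its result.

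**The case against.** The strongest reply is that the planned between-arm safety comparison is not a serious-event comparison. Section 21.3 compares all related events at any grade, section 25.5 lists every premature discontinuation with group and reason, and section 21.7 records dose reductions, interruptions and cessations. A reader might infer from the mismatch that the trial's safety comparison undercounts propranolol's harms. The documents do not support that, because these infants are counted in 21.3. What remains is that 21.3 does not separate recurrent or terminating events from a single mild one, and the serious-event tally omits them below grade 3.

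A reader might also infer that the serious-event rate is tilted against atenolol. That does not follow either. Intolerable CNS effects count at any grade and are expected less often on atenolol, and nothing in the documents says that persistent hypotension or bradycardia is expected more often on it.

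It can also be said that a classification and a stopping rule need not coincide; grade 3 events and CNS effects are serious without mandatory termination. That is fair, and full agreement is not required. But a condition that ends participation for safety is a natural candidate for the serious list. The plan treats two such conditions that way and a third only from grade 3, without explanation.

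Finally, the terms recurrent and persistent are not defined in section 21, so adding them to 21.6 brings in an undefined term. This stands and is dealt with in the fix.

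**Conclusion.** Sections 21.6 and 21.8 are inconsistent for one class of events and should be reconciled. Serious-event counts by arm may understate a beta-2 difference, because recurrent or persistent hypoglycemia and bronchial events of grade 1 or 2 are left out. The all-adverse-event comparison keeps these infants but hides the recurrence or persistence that triggers termination.

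The size is unknown. On the assumed rates above, the shift in the serious-event rate difference runs from nothing to about 4 percentage points, with 0.9 to 9.0 infants left out on propranolol and 0 to 1.8 on atenolol. The upper figures are the extreme of an assumed range, not an estimate. How many such events would stay below grade 3 depends on CTCAE v4.0 criteria that the documents do not reproduce. The net direction of the effect on the total serious-event rate cannot be derived.

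The primary noninferiority analysis is not shown to be affected. Section 19 refers to withdrawal for severe adverse events as treatment failure, and one might read that through 21.6, but the plan does not equate the two terms. This is a cheap improvement to safety reporting.

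**What to change.** - In 21.6, add hypoglycemia, bronchitis with dyspnea, bronchial hyperreactivity and bronchospasm, when recurrent or persistent, to the serious-event list. State that the words carry the same meaning as in 21.8, and write that meaning down once so that both sections refer to it.
- Report serious events by arm in total and by component: hemodynamic, metabolic or bronchial, CNS, and other events of grade 3 or higher. The components show where any difference lies, which the total cannot.
- Turn the discontinuation listing in 25.5 into a table of mandatory terminations by arm and reason.

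This concerns the reporting definition only; the termination rule in 21.8 does not change. The cost is one list entry, one shared definition and two small tables, built from adverse event and discontinuation data that the plan already records. If recurrence or persistence was not recorded in a usable form, those records would need review against the written definition. The reported serious-event rate may rise slightly.

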**16 Study visits**

Study visits were scheduled at enrolment; at 1, 4, 12, and 24 weeks after treatment; and then every 12 weeks until the end of the study or if there was any specific need after enrolment. Body weight, height, heart rate, blood pressure, blood glucose, full blood count, liver function tests, renal function and ECG were obtained during protocol visits and in-between periods if needed. All adverse events, which were identified by the investigators as at least possibly treatment-related during the 24-week treatment phase, were collected by the investigator. At each visit, the drug will be handed over to the parent/guardian in an amount sufficient to last the interim duration.

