## 17 Treatment

### 17.1 Standard case management

| Arms                                 | Assigned Interventions  |
|--------------------------------------|---|
| Active
Comparator:
Propranolol | 
Drug: Propranolol
 
Initiated at a dosage of 1 mg/kg per day divided 3 times daily for 1 week and then increased to 2 mg/kg per day divided 3 times daily from week 2.
 
2 mg/kg per day in 3 doses from week 2 after a gradual increase in the dose in the first week.
 
Other Name: None
 |
| Active
Comparator:
Atenolol    | 
Drug: Atenolol
 
Initiated at a dosage of 0.5 mg/kg per day in a single dose for 1 week and then increased to 1 mg/kg per day in a single dose from week 2.
 
1 mg/kg per day in a single dose from week 2 after a gradual increase in the dose in the first week
 
Other Name: None
       |

In the propranolol group, propranolol was initiated at a dosage of 1.0 mg/kg per day divided 3 times daily for 1 week and then increased to 2 mg/kg per day divided 3 times daily from week 2. The treatment schedule was at least 6 months.

In the atenolol group, atenolol was initiated at a dosage of 0.5 mg/kg per day in a single dose for 1 week and then increased to 1 mg/kg per day in a single dose from week 2. The treatment schedule was at least 6 months.

Patients were administered the first dose of  $\beta$ -blocker at 8:00 am. During  $\beta$ -blocker treatments, the dose was adjusted for weight gain. At the end of treatment, the drug dose was adjusted according to the tapering schedule, which was determined by investigators and was supposed to be 4 weeks.

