### ***17.2 Rebound management***

Significant rebound after stopping the medication was treated by reinstitution of daily therapy with either propranolol (2 mg/kg per day) or atenolol (1 mg/kg per day) until hemangioma remission.

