### ***21.3 Collection and management of adverse events***

The frequency of adverse events (e.g., sleep disturbance, cool or mottled extremities, diarrhea, etc.) were collected by the investigator and reported by parents. The investigators collected any untoward medical occurrence in the form of signs, symptoms, abnormal laboratory findings, or diseases that emerged or worsened relative to baseline assessment. All adverse events that were identified by the investigators as at least possibly treatment-related (treatment-emergent adverse events or adverse events that have worsened since baseline) were included in the analysis. For each adverse event, the percentage of subjects who experienced at least 1

---

occurrence of the given event was summarized by treatment group. Adverse events during the initial 24-week treatment phase were compared between the two groups.

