**22 Tapering and discontinuation of treatment**

Propranolol or atenolol were tapered and stopped at an appropriate time, which was primarily based on the response and lesion regression after treatment. In this trial, the treatment was tapered and discontinued on complete or nearly complete resolution of IH or if no further improvement of IH (for 12 weeks of observation) was observed after month 6. At the end of the treatment period, the drug dose was gradually reduced over 4 weeks and then cease. For more detail regarding the procedures for tapering and discontinuation of treatment, refer to the **Treatment** section.

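### The serious adverse event definition and the between-arm safety comparison stop at about month 6, while treatment can continue, taper and restart after it

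*Combined protocol and SAP*

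**What the plan says.** Three sections of the combined protocol and SAP set the safety window.

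- Section 21.6 (grading): "A serious adverse event is defined as any of the following toxicities identified during the 6 months of treatment". The list that follows is grade 3 or higher events, persistent hypotension, persistent bradycardia and intolerable CNS effects.
- Section 16 (study visits) describes the events that investigators identified "as at least possibly treatment-related during the 24-week treatment phase, were collected by the investigator".
- Section 21.3 (collection and management): "Adverse events during the initial 24-week treatment phase were compared between the two groups".

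Four other sections set exposure and follow-up.

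- Section 17.1, for each arm: "The treatment schedule was at least 6 months". No maximum is given.
- Section 22 allows tapering and stopping on resolution, or "if no further improvement of IH (for 12 weeks of observation) was observed after month 6". At the end of treatment, "the drug dose was gradually reduced over 4 weeks and then cease".
- Section 17.2: "Significant rebound after stopping the medication was treated by reinstitution of daily therapy", continued until remission. Section 20.5 also recommends restarting systemic therapy.
- Section 9 follows each infant for 96 weeks. Section 16 schedules visits every 12 weeks after week 24.

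**The concern.** The safety window is shorter than the exposure that the plan itself provides for. An infant can be on study drug in month 7 or 8, in the taper, or back on daily therapy after rebound. A grade 3 or higher event at that time does not meet the definition in section 21.6 and is in no planned comparison.

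Section 21.8 makes the mismatch plain. It requires termination for any grade 4 or higher event, for persistent hypotension and for persistent bradycardia, with no time limit. An event in month 8 can therefore force termination and still not be a serious adverse event.

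The protocol outline names safety beside efficacy as the trial's purpose, and section 5 rests the case for atenolol largely on fewer adverse effects. Time on drug after week 24 depends on response (section 22) and on rebound (section 17.2), so it may differ between the arms. If it does, a count cut off at month 6 leaves out more late events from the arm with more late exposure.

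**Working it through.** The plan gives no figure for exposure after week 24, so there is none to reproduce. The check compares the window with the plan's own durations.

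**Inputs**

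- Safety window: 24 weeks (sections 16 and 21.3). Section 21.6 says 6 months. The plan uses week 24 and 6 months for the same primary assessment, so both are taken as 24 weeks here. Six calendar months would be 182.625/7 = 26.1 weeks, about 2 weeks longer.
- Minimum treatment: 6 months, taken as 24 weeks (section 17.1).
- Taper: 4 weeks (sections 17.1 and 22).
- Observation without improvement: 12 weeks (section 22).
- Follow-up: 96 weeks (section 9).

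**Formula.** With T weeks on drug in total, the share outside the window is (T − 24)/T.

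| Case | T (weeks) | Weeks outside | Share outside |
|---|---|---|---|
| Taper falls within the six months | 24 | 0 | 0% |
| Taper added after month 6 | 24 + 4 = 28 | 4 | 4/28 = 14.3% |
| 12-week observation starts at month 6, then taper | 24 + 12 + 4 = 40 | 16 | 16/40 = 40.0% |
| Assumed 48 weeks on drug | 48 | 24 | 50.0% |
| Ceiling: on drug for all of follow-up | 96 | 72 | 75.0% |

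The last two rows are illustrations, because the documents state no mean or maximum duration. Retreatment after rebound adds to T in any row, and the documents give no expected rebound rate.

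**What this means in events (illustration only).** Assume a constant event rate on drug, 180 infants per arm all treated for T weeks, and a serious-event risk r of 1% to 5% over 24 weeks.

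- Expected inside the window: 180 × r = 1.8 to 9.0 per arm.
- Expected outside it: 180 × (r/24) × (T − 24). This is 0.3 to 1.5 per arm at T = 28 and 1.2 to 6.0 at T = 40.

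**Does any other section extend the window?**

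- Section 21.2 takes adverse event data at scheduled or unscheduled visits, with no week limit. It concerns recording and plans no comparison.
- Section 21.5 assesses causality for events after administration, again with no week limit and no comparison.
- Section 25.5 defines the safety population by receipt of a dose but sets no observation period.
- The adverse event row in section 14 shows no readable extent in the text available.

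None of these plans a comparison of adverse events after week 24.

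**The case against.** A fixed 24-week comparison is a sound choice. It gives both arms the same planned window, whereas exposure after week 24 depends on response. That stands, and it is a reason to keep the 24-week table as the main one. It does not justify a time limit inside the definition of seriousness.

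Three stronger readings are tempting, and the documents support none of them.

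- *Late serious events are not recorded at all.* Section 16 points that way, but sections 21.2 and 21.5 have no week limit, section 25.5 lists every premature discontinuation by arm and reason, and the extent of the section 14 row cannot be read. What is shown is that late events are neither labelled serious nor compared.
- *Every infant has on-drug time outside the window.* Infants can stop before month 6 through withdrawal for nonresponse or severe adverse events (section 19), discontinuation for intolerable CNS effects (section 21.7), or mandatory termination or free withdrawal (section 21.8). Even for those who complete six months, the text does not say whether the taper is added to that period or falls within it. The 12 weeks in section 22 may also be a look-back made once month 6 has passed, and resolution is a separate trigger with no 12-week wait.
- *The comparison favours one drug.* Nothing in the documents shows that either drug needs longer treatment or more retreatment.

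One further caution stands. Section 17.2 names both drugs and does not say that the one restarted is the randomised one. A late event rate by randomised arm alone could attribute one drug's events to the other arm.

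**Conclusion.** The point holds for what is counted and compared. As written, a grade 3 or higher event on drug after month 6 is not a serious adverse event and is in no planned comparison, although some such events may still be recorded.

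For infants who complete six months and then taper, the on-drug time outside a 24-week window is about 14% if the taper follows month 6. It is 40% if the 12-week observation also starts at month 6, and more with longer treatment or retreatment. These are shares for individual courses of treatment. No average for the trial population can be derived, because the documents give no mean duration or rebound rate. The direction of any effect on the comparison is unknown.

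The point does not touch the primary efficacy analysis. It should be corrected because safety is part of the trial's stated purpose and the correction is cheap.

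**What to change.** 1. In section 21.6, remove the six-month limit so that the definition applies from first dose to week 96, including continued treatment, taper and retreatment.
2. Amend sections 16 and 21.3 so that collection covers the same period, and reconcile them with sections 21.2 and 25.5. Changing section 21.6 alone would leave section 16 describing collection in the 24-week phase only. State in section 25.5 the observation period for the safety population, and use either weeks or months throughout.
3. Keep the 24-week between-arm comparison as the main, equal-window table.
4. Add a supplementary table of serious events to week 96, as counts and per patient-year on drug, by randomised arm and by drug actually received.

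The cost is a wording amendment and modest extra recording at the 12-weekly visits already scheduled. Time on drug can largely be built from the dose interruptions and cessations recorded under section 21.7 and the discontinuation times needed for section 25.4. Restart dates and the drug restarted must also be captured. The later comparison will be descriptive, because exposure after week 24 depends on response. Dosing and clinical management do not change.
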